Please note the primary difference between the current proposal and the original application. In the original application, the target site was Gateway Residential Services (GRS). By the end of the study, the facility changed its name to the Caritas ARTS Program. In addition, we added a second site after consultation with the Project Officer, both to ensure we met the pre-specified recruitment target and to enable us to inform the design of a fully powered trial. The two programs are:

Caritas ARTS Program – short term residential facility with 16 beds, average length of stay 6-10 days

Rosecrance Health Network – long term residential facility with 80 beds, average length of stay 30-45 days

C. SPECIFIC AIMS AND DETAILED STUDY METHODOLOGY

1. Specific Aims

The goal of this pilot study is to adapt the delivery of PW for a new population (parents of ASUD preparing for discharge) and new setting (residential treatment), and to obtain initial data on its feasibility, acceptability, and effectiveness. The study began with an open trial of 10 parents to demonstrate feasibility, acceptability, and preliminary evidence of effectiveness over time.

Specific research aims of the protocol are:

Aim 1: To examine the feasibility and acceptability of an adapted PW intervention that includes moderate engagement strategies for parents of ASUD preparing for discharge from residential.

Hypothesis 1a: Adapted PW will be both feasible and acceptable to parents. Feasibility will be indicated by enrollment rates ($\geq 80\%$) and indicators of parent engagement: attendance of ≥ 2 coaching sessions for $\geq 75\%$ of parents, and online usage patterns of 2+ PW logins, viewing of video vignettes embed in text messages, 1+ parent board posts. Criteria for acceptability will be withdrawal rates ($\leq 20\%$), $\geq 80\%$ of ratings on a consumer satisfaction scale in the highest two categories, and positive feedback from exit interviews with parents.

Secondary Aims 2-4: To examine the preliminary effectiveness of the experimental intervention on: substance use outcomes, related high-risk behaviors, and parenting skills (the putative mediators of change).

Hypotheses: At baseline, 6-week follow up, 12-week follow up, and 24-week follow-up, the experimental intervention will demonstrate superior outcomes, relative to treatment as usual on:

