- 2a: indicators of substance use: substance use frequency, severity of substance use symptoms, rates of relapse, and biological markers (i.e., urine drug screens).
- 3a: high-risk behaviors commonly related to substance use: externalizing behavior, sexual risk behavior, school truancy, and criminal behavior.
- 4a: parenting behaviors: parental monitoring and communication, as demonstrated by both parent and adolescent report and observed during an in vivo task.

2. Detailed Study Methodology

STUDY PURPOSE. We are seeking approval to conduct a randomized control trial of 60 parents whose adolescents are preparing for discharge from residential substance use treatment at a new remote site. The goals of this project are to: (1) examine if the adapted intervention and the study assessment procedures are feasible and acceptable to study participants; (2) evaluate the preliminary effectiveness of the adapted intervention.

STUDY POPULATION. We are currently seeking approval to enroll 60 parent-adolescent dyads (i.e., a total of 12- participants) for a randomized trial.

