Inclusion / Exclusion Criteria. Parents must meet the following **inclusion criteria**: (1) be the parent or legal guardian of an adolescent aged 12 years -17 years inclusive, at the start of the project; (2) had adolescent admitted to residential treatment facility due to concerns about frequency and/or severity of substance use; (3) will be the primary guardian living with the adolescent after the adolescent's discharge from treatment; (4) access to internet and a phone that can receive text messages; (5) fluent in English or Spanish; and (6) willing to provide written consent and teen willing to provide written assent. Adolescents automatically qualify for the study if their parents meet the aforementioned criteria. There are no exclusion criteria for participation in this study beyond failure to meet the inclusion criteria. If during the consent or assent process, the teen exhibits any conditions or behaviors that would preclude participation in the baseline assessment (e.g., mania, psychosis), then the interview will be paused and the research staff member conducting the consent / assent process will immediately notify the Medical or Clinical Director ([name] at Caritas, [name] at Rosecrance) at the residential facility to ensure adequate clinical assessment of the adolescent. The interview will be rescheduled for a time when residential staff has determined that the adolescent can participate in an interview. Behaviors that would cause a delay in the interview are expected to occur with extreme rarity, as there is no access to substances within the residential center and adolescents with acute conditions such as mania and psychosis are typically not admitted to the residential center.

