Retention procedures. At baseline, multiple sources of contact information will be recorded for parents and ASUD to prevent attrition. A demographic form will be administered aloud by a research staff member at Brown via Zoom and information will be obtained and stored in hard copy form in locked filing cabinets in the PI's office at Brown University. Contact information will be updated by periodic phone calls and during assessments. Reminders will be made via phone and mail. The PI will hold weekly case review meetings to review no-shows and outreach attempts, and discuss plans to complete contact with missing participants. Compensation for completion of questionnaires and interviews/discussions escalates slightly from \$40 at baseline, 6 and 12 weeks to \$60 at 24 week followThis compensation schedules recognizes the increased effort associated with scheduling a follow-up and providing a urine screen after the teen has been discharged. We have used these retention procedures (e.g., reminder calls, periodic update calls, escalating compensation) with success in current and prior projects.

Randomization. In the randomized pilot trial, parent-adolescent dyads will be randomized to the adapted PW condition or to residential treatment as usual using urn randomization balanced by biological sex (male vs female), race/ethnicity (White, Non- Hispanic vs Non-White, Hispanic), and days of substance use (1-45 vs 45+). Randomization will be done by the research staff using a randomization spreadsheet immediately at the end of the baseline assessment; condition assignments will then be immediately told to the family. Those assigned to the adapted PW condition will be scheduled for their first remote coaching session approximately 4 weeks prior to discharge (described below).

Protecting confidentiality. Steps taken to protect the confidentiality of participants are detailed in **Section D, “Possible Risks and Anticipated Benefits”** in the paragraphs focused on minimizing risk of loss of confidentiality.

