MEASURES. Parents and teens will complete a baseline assessment either immediately after providing informed consent / assent or shortly thereafter via phone or video conference by Brown University staff. Follow-up measures will also be conducted by phone or video conference by Brown University staff at 6, 12, and 24 weeks following the teen's discharge. The baseline assessment will be about 1.5 hours for the adolescent and 1 hour for the parent and the follow-up assessments will be about 1.5 hours for both the adolescent and parent. Parents and adolescents have been able to complete assessments of this length or longer in our team's prior and current studies.

The measures used in this study are outlined below. Based on our team's experience working with 100s of families on clinical research projects in Rhode Island, we have decided to translate all of the **parent** measures into Spanish. We retain all of the adolescent measures in English. It is well established that adolescents tend to acculturate to the U.S. culture more quickly than their parents, and we have found that adolescents in our studies from Spanish-speaking families are typically comfortable speaking and completely measures in English or Spanish, while parents tend to prefer to speak in Spanish. If adolescents prefer to speak in Spanish, we will use a translator to administer all of the adolescent measures aloud.

Rationale for Measures: Aim 1. To address Aim 1, we will assess feasibility and acceptability.

Feasibility. PW feasibility will be assessed based upon the percent of parents willing to participate as well as indicators of parental engagement, including: number of coaching sessions attended before teen's discharge, number of coaching sessions attended after discharge, number of PW logins, number of PW online sessions completed, amount of time spent logged into PW program, number of logins to the parent message board, number of questions posted to the message board, and amount of time spent logged into the board.

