By using the GAIN at follow-ups, we will capture continuous data on the teen's use and high-risk behaviors following discharge. We will also include measures of parental communication and monitoring (Aim 4), as these outcomes are not included in the GAIN and parenting practices are a key factor associated with ASUD. PI [name] is a certified GAIN trainer and has experience analyzing GAIN data. Specific scales that we will analyze to address Aims 2 and 3 are described below.

Demographics. The GAIN Background section collects routine socio-demographic variables including age, sex, ethnicity, race, and grade in school. Items in other GAIN sections indicate the teen's history of substance use or mental health treatment utilization, data that will be used to control for additional treatment received.

Substance Use. The following GAIN items/scales and biological markers will address Aim 2 (substance outcomes).

Days of Use (Past 90 Days). A series of GAIN items evaluate days of substance use over the past 90 days. These items have shown excellent comparability to the well-validated Timeline Follow-Back Interview (TLFB). Like the TLFB, the GAIN assesses days of alcohol and drug use using a calendar with temporal cues (e.g., holidays, special events) to facilitate recall. We will analyze three variables, separately for alcohol, marijuana, and other drugs: total number of use days, total days abstinent, and latency to first use.

Substance Frequency Scale (SFS). The SFS scale averages the percent of days in the past 90 during which there was use of alcohol, marijuana, or heavy drugs; use to intoxication; and failure to perform activities due to use. This scale has good reliability ($\alpha = .85$) and predicts substance-related problems as well or better than biometric (e.g., urine) markers of use.

Biological markers. Biological markers will **only be used at the follow-up assessments (6, 12, and 24 weeks)**, since adolescents are not expected to have access to substances at the time of the baseline assessment (likely to be at least 1-2 days after admission). 8-panel urine screens that detect the presence of marijuana, cocaine, amphetamines, methamphetamines, MDMA, opiates, oxycodone, and benzodiazepines mailed to each family and administered to the teens by the parents will be used to provide a biological indicator of abstinence. Teens who present as acutely intoxicated based on researcher observations, parent-report, or adolescent-report will be rescheduled.

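### The 90-day GAIN recall reaches back before discharge for 48 of 90 days at week 6 (6 at week 12, 0 at week 24), so the follow-up trajectory compares scores with different post-discharge exposure

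*Combined protocol and SAP*

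**What the plan says.** The MEASURES section sets the visits: "Follow-up measures will also be conducted by phone or video conference by Brown University staff at 6, 12, and 24 weeks", counted from the teen's discharge. Under Substance Use, Days of Use, the recall is fixed: "A series of GAIN items evaluate days of substance use over the past 90 days". The SFS is an average of percentages over the same 90 days. The sexual behaviour items also look back 90 days, as do the school and legal day counts.

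The rationale for Aims 2-4 says that the GAIN at follow-up captures behaviour after discharge. The Data Analysis Plan for Aims 2-4 declines to start trajectories at baseline because the abstinent residential stay would mislead. It compares trajectories over the follow-up period instead, with baseline status as a covariate. The listed covariates are baseline status on the outcome, baseline group differences and other treatment received. Neither site nor length of stay is named.

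Section B describes two sites: one is a "short term residential facility with 16 beds, average length of stay 6-10 days", the other a "long term residential facility with 80 beds, average length of stay 30-45 days". The Data Analysis Plan puts the stay at about 3.5 months.

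Hypothesis 2a covers "indicators of substance use: substance use frequency, severity of substance use symptoms, rates of relapse, and biological markers". No time origin is given for relapse, or for latency to first use.

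**The concern.** The first follow-up comes after 42 days, but its questions look back 90. The week-6 score therefore mixes behaviour after discharge with days in residence and, at the Section B stays, with days before admission. This runs against the stated purpose of the follow-up GAIN. It also brings back into the trajectory the stay that the plan removed by dropping baseline.

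Three visits that look alike (use days out of 90) carry 42, 84 and 90 days on which a post-discharge effect could show. Comparing them over time confounds change in behaviour with change in exposure. These are pilot estimates, but the plan's main analytic goal is effect sizes with 95% confidence intervals, and those are to inform the size of the next trial.

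**Working it through.** **Inputs from the documents.** Visits at 6, 12 and 24 weeks after discharge; a 90-day window; average stays of 6-10 and 30-45 days (Section B) or about 3.5 months (Data Analysis Plan). The plan states no pre-discharge share, so there is no figure to reproduce.

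**Step 1: exposure.** Pre-discharge days = max(0, 90 − 7 × weeks).

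| Visit | Day | Pre-discharge | Post-discharge | Post share |
|---|---|---|---|---|
| Week 6 | 42 | 90 − 42 = 48 (53%) | 42 | 0.47 |
| Week 12 | 84 | 90 − 84 = 6 (7%) | 84 | 0.93 |
| Week 24 | 168 | 0 | 90 | 1.00 |

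This is exact for on-schedule visits; an early or late visit shifts it day for day.

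**Step 2: what the 48 week-6 days are.** In-residence days = min(48, stay); pre-admission days = the rest.

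- Stay 6-10 days: 6-10 in residence, 38-42 before admission.
- Stay 30-45 days: 30-45 in residence, 3-18 before admission.
- Stay of about 3.5 months: 48 in residence, none before admission.

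At week 12 the 6 days are all in residence at any of these stays.

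**Step 3: arm difference in raw units.** A constant difference D in the proportion of post-discharge days reads D × 42/90 = 0.47D, D × 84/90 = 0.93D and 1.00D. With D = 10 points (assumed) this is 4.7, 9.3 and 10.0.

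For an effect of 20 points to day 42 and 10 points after (assumed):

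- out of 90: 20 × 42/90 = 9.3; (20 × 42 + 10 × 42)/90 = 14.0; 10.0;
- on post-discharge denominators: 20; (840 + 420)/84 = 15; 10.

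The fade is hidden in the first line and visible in the second.

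**Step 4: level trend with unchanged behaviour.** Week-6 use days = (48 − stay) × pre-admission rate + 42 × post-discharge rate, with no use in residence. Week 12 = 84 × post-discharge rate.

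| Assumed rates | Stay 6-10: week 6 | Stay 30-45: week 6 | Week 12 |
|---|---|---|---|
| 70% before, 30% after | 42.0 to 39.2 | 25.2 to 14.7 | 25.2 |
| 25% before, 30% after | 23.1 to 22.1 | 17.1 to 13.4 | 25.2 |

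In the first row the false week 6 to 12 change at short stays is a fall of 16.8 to 14.0 days; in the second it is a rise of 2.1 to 3.1 days.

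**Step 5: standardised effect at week 6, by simulation.** All rates are assumed: beta-distributed use (precision 3), 35% against 25% after discharge, 70% before admission, correlation 0.4, baseline 90-day score as covariate, stays uniform within each site's range, sites 50/50 with equal post-discharge use. The sample-size ratio is (d on post-discharge days / d on 90 days) squared.

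| Analysis | Ratio | Range over 27 input sets |
|---|---|---|
| Short-stay site alone (d 0.45 to 0.44) | about 1.05 | 1.02-1.10 |
| Long-stay site alone (d 0.45 to 0.42) | about 1.15 | 1.06-1.31 |
| Pooled, no site term (d 0.45 to 0.29) | about 2.4 | roughly 1.6-4.5 |
| Pooled, site term | about 1.2 | 1.14-1.33 |
| Pooled, site-specific baseline slopes | about 1.1 | 1.05-1.20 |

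The sets vary correlation (0.2, 0.4, 0.6), pre-admission use (50, 70, 85%) and precision (1.5, 3, 5). The pooled loss without a site term arises because the pre-admission share of the window differs sharply between sites and enters as unexplained variance.

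**The case against.** The strongest reply is that randomisation protects the contrast. "Randomization will be done by the research staff using a randomization spreadsheet immediately at the end of the baseline assessment", so pre-admission days precede assignment and balance in expectation. For in-residence days the protocol says "there is no access to substances within the residential center", so those add no use in either arm. This stands: a reader might infer that the week-6 arm difference is biased, and the documents do not support that. It is diluted.

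A second reply is that the plan targets standardised effects, on which much of the distortion disappears. Within a site this is largely right: under the Step 5 type of assumptions, the halving effect reads about 0.95, 0.70 and 0.45 at the short-stay site and 0.90, 0.70 and 0.45 at the long-stay site, so the fade stays visible. But the mixed models are fitted to the outcomes as scored, and the listed model pools the sites without a term for them.

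A reader might also infer from the 70%/30% row that the false trend always runs in opposite directions at the two sites. It does not: the 25%/30% row rises at both. The documents give no use rates, so a reversal is one scenario.

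Calendar-assisted recall may let staff recover days since discharge. The plan does not say that they will. Finally, the affected aims are "Secondary Aims 2-4: To examine the preliminary effectiveness of the experimental intervention on: substance use outcomes" and related behaviours, in a pilot of 60 dyads. That limits the consequence without removing the inconsistency. Urine screens and the parenting measures are not described as 90-day recall and are outside this point.

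**Conclusion.** The point holds and should be fixed. The 48, 6 and 0 pre-discharge days follow from the documents alone and do not depend on which length of stay is correct. The raw-scale dilution (0.47, 0.93, 1.00) follows for any effect that is constant over post-discharge days. It is serious at week 6 and slight at week 12.

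The composition of the 48 days depends on length of stay, on which Section B and the Data Analysis Plan disagree. The size and sign of the false level trend depend on assumed use rates as well. The standardised figures rest wholly on assumed inputs. The contrast among them is more informative than any single value: a modest loss within site or with a site term, and a large one (about 2.4) in the pooled model as listed. That last figure assumes equal post-discharge use at both sites and an even split, so it should not be read as a forecast for this trial.

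**What to change.** 1. At week 6, score the day-count use and risk items for days since discharge. Use the GAIN calendar if it allows; otherwise add a short since-discharge form.
2. Analyse these as a proportion of post-discharge days in the window: 42 at week 6; 84 at week 12 where the stay was at least 6 days (Section B gives averages, so check individual stays); 90 at week 24. Use actual days when visits are off schedule.
3. State that the 84-day week-12 window contains the whole week-6 window. In Step 3 this is why week 12 reads 15 when the effect in that interval is 10. If interval-specific effects are wanted and the calendar allows, use since-last-visit intervals of 42, 42 and 84 days.
4. Restrict number of partners and recency of last sex to the post-discharge period; do not turn them into proportions.
5. Measure relapse and latency to first use from the discharge date.
6. Keep the standard 90-day scores as descriptive for comparison with norms, and leave the week-6 90-day SFS out of the trajectory if it cannot be re-anchored.
7. Reconcile the lengths of stay in Section B and the Data Analysis Plan.

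The cost is some added interview time at week 6, derived variables and analysis-plan wording. Re-scored values are not comparable with the 90-day norms, which the protocol regards as a major advantage of the GAIN; item 6 keeps that comparison available.

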High-Risk Behaviors Related to Substance Use. The following GAIN items/scales will address Aim 3. These specific scales have been selected based on the well-documented association between adolescent substance use and externalizing behavior, school truancy, high-risk sexual behavior, and criminal behavior.

Risky Sexual Behavior. The GAIN contains a series of items that assess sexual behavior over the past 90 days. Specific data obtained includes: number of partners (male and female), number of sexual contacts, number of times had unprotected sex, and recency of last sex.

Days of School Attendance. Using a 90-day recall, the GAIN assesses number of days the

teen: attended school, was absent from school due to illness, and intentionally skipped school. The method is comparable to that used in the Days of Use substance use items.

Days of Legal Involvement. Using a 90-day recall, the GAIN assesses number of days the teen: did something, other than drug use, that would have gotten them into trouble with the police and number of days the teen was on probation, on parole, in juvenile detention, or in jail.

Parenting. We use the measures below to address Aim 4, which tests the effects of PW on parental monitoring and communication. We use self-report measures with strong psychometric properties, as well as in-vivo assessment to increase the comprehensiveness of our assessment. If a parent loses custody after the teen's discharge, we will not administer the parenting measures at the subsequent follow-up (treating parent data as missing). Based on prior protocols, we expect parent data loss of less than 5% with this approach.

Parent Monitoring Questionnaire (PMQ). The PMQ is a 24 item youth and parent report measure designed to assess parental monitoring and sources of parental knowledge. The monitoring subscale has demonstrated good reliability ($\alpha = .82$ parents, $.85$ youth) and correlates with adolescent internalizing and externalizing maladjustment, deviant peer relationships, and family discord.

Parent-Adolescent Communication Scale (PACS). The PACS is a youth and parent report measure that assesses positive and negative aspects of general parent-teen communication and the content and process of parent-teen interactions. The two subscales have good reliability ($\alpha = .77 - .88$) and have been shown to correlate with teen engagement in risk behavior.

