discharge and ≥ 1 of 2 sessions post-discharge for $\geq 75\%$ of parents, and online usage patterns of 3+ PW logins, 2+ parent board logins, and 2+ hours logged in for $\geq 75\%$ of parents. Criteria for acceptability include withdrawal rates ($< 20\%$), satisfaction ratings ($\geq 80\%$ of CSQ items rated “agree” or “strongly agree”) and positive feedback from the exit interviews with parents and therapists. Criteria will be finalized based on parent and staff feedback in Phase 1.

Aims 2 - 4. The dependent variables (DVs) include substance use (Aim 2), related high-risk behaviors (Aim 3), and parental monitoring and communication (Aim 4, putative mediators). By nature of residential treatment, we expect teens’ level of substance use and risk behavior to start high at intake, drop off for the duration (~ 3.5 months) of treatment and then increase over the follow-up period. Trajectories that begin at baseline would be misleading, since all teens will have a sustained period of abstinence (with minimal variance). We therefore compare trajectories of use over the follow-up period, while controlling for baseline status as covariates.

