We will begin by comparing the DV scores (means of continuous DVs and percentages of categorical DVs) at each assessment. We will conduct separate mixed models predicting each DV by condition, controlling for the following covariates: baseline status on the DV, baseline differences between groups, and any mental health or substance use treatment received over the follow-up period. We will analyze the effect of PW dosage on each DV and calculate partial eta squared (η^2) to estimate the proportion of variance caused by PW. We are underpowered to test mediation, but will examine the effects of PW on our putative mediators (Aim 4), and correlations between change in the mediators and change in the primary outcomes (Aims 2-3), with the goal of finding promising trends to pursue in a larger trial. We will cautiously attempt more sophisticated analyses using hierarchical modeling, a flexible approach to analyzing change that has been frequently used by the PI [37, 90, 91]. Mixed models are ideally suited to address Aims 2-4, by enabling us to compare the conditions at each time point while accounting for the correlation of observations over time. Although convergence is challenged in a small sample, it is feasible. Our primary goal will be to provide measures of association and 95% confidence intervals to reveal the ES of PW on each DV.

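### The week-12 90-day counts include every post-discharge day already counted at week 6, so week 12 is cumulative and the week 6-to-12 trajectory is distorted

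*Combined protocol and SAP*

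**What the plan says.** Under Measures (section C.2), the visit schedule is: "Follow-up measures will also be conducted by phone or video conference by Brown University staff at 6, 12, and 24 weeks", counted from the teen's discharge.

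The GAIN outcomes for Aims 2 and 3 look back a fixed 90 days:

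- Days of Use: "A series of GAIN items evaluate days of substance use over the past 90 days". Total use days and abstinent days are analysed by substance.
- Substance Frequency Scale: "The SFS scale averages the percent of days in the past 90 during which there was use of alcohol, marijuana, or heavy drugs", with intoxication and failure to perform activities as further components.
- Risky Sexual Behavior: "The GAIN contains a series of items that assess sexual behavior over the past 90 days".
- School attendance and legal involvement: "Using a 90-day recall, the GAIN assesses number of days the" teen spent in each state.

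The Data Analysis Plan for Aims 2-4 leaves baseline out of the trajectory: "We therefore compare trajectories of use over the follow-up period, while controlling for baseline status as covariates". It favors mixed models "by enabling us to compare the conditions at each time point while accounting for the correlation of observations over time". The hypotheses in section C.1 expect superiority at each follow-up. No section shortens the recall to the time since the last visit, splits the calendar at visit or discharge dates, or mentions overlapping windows.

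**The concern.** A 90-day look-back taken 42 days after the previous one must cover much of the same ground. The week-12 score is then not a fresh observation of weeks 7 to 12, although a comparison at each time point and a trajectory across time points invite that reading.

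What is at stake is the time course of any effect: whether a benefit fades once the teen has been home for six weeks, holds, or emerges later. The Data Analysis Plan names effect sizes with 95% confidence intervals as its main goal, and the sample-size section uses the detected effect to size a larger trial. The plan also predicts that use will rise after discharge, so a rise created by the window would look like confirmation.

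**Working it through.** The plan states no figure for overlap, so there is none to reproduce. The inputs are visits at 6, 12 and 24 weeks after discharge (days 42, 84 and 168, with discharge as day 0) and a recall of 90 days, both from Measures.

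**Windows.** A 90-day window ending on day t covers days t − 89 to t.

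| Visit | Window (days) | Up to discharge | After discharge |
|---|---|---|---|
| Week 6 | −47 to 42 | 48 | 42 |
| Week 12 | −5 to 84 | 6 | 84 |
| Week 24 | 79 to 168 | 0 | 90 |

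**Overlap.** Weeks 6 and 12 share days −5 to 42, which is 48 of 90 days (53%). This includes all 42 post-discharge days of week 6, which make up 42/84 = 50% of the post-discharge days at week 12. Weeks 12 and 24 share days 79 to 84, which is 6 of 90 (7%). Weeks 6 and 24 share none.

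Cutting every window at discharge does not remove the overlap: week 6 becomes days 1-42 and week 12 becomes days 1-84. A week-12 visit up to 6 days late still re-counts all 42 days; at 14 days late it re-counts 34.

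**Effect on an arm difference, in days.** Take a difference of 0.10 use days per day.

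- Only on days 1-42: week 6 = 0.10 × 42 = 4.2; week 12 = 0.10 × 42 + 0 × 42 = 4.2. As a percent of 90 days, both are 4.2/90 = 4.7%.
- Only on days 43-84: week 6 = 0; week 12 = 0.10 × 42 = 4.2.

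The week-12 score is the same 4.2 in both cases, although the arms are equal in weeks 7-12 in the first.

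**Effect on a trajectory.** Take use on 10% of days after discharge and none before: 0.10 × 42 = 4.2, 0.10 × 84 = 8.4 and 0.10 × 90 = 9.0 days.

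**What the week 6-to-12 change measures.** In the difference of the two counts, the 48 shared days cancel. What remains is days 43 to 84 minus days −47 to −6. The change therefore compares weeks 7-12 with 42 days before discharge, and weeks 1-6 drop out.

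How many days of the week-6 window precede admission depends on length of stay (48 minus the stay, or zero if negative):

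- 38 to 42 days for the 6-10 day stay at the short-term site;
- 3 to 18 days for the 30-45 day stay at the long-term site;
- none for the stay of about 3.5 months assumed under Aims 2-4.

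The illustration with no use before discharge fits the last case best. If use before admission was heavy, the apparent rise would shrink or reverse. The site descriptions and the analysis plan disagree on duration and must be reconciled.

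**Correlation from overlap alone.** If daily use were independent with equal variance, the week 6/week 12 correlation would be 48/90 = 0.53 over the full windows, or 42/√(42 × 84) = 0.71 if only post-discharge days vary. These are illustrations, not estimates.

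**The same cases on separate intervals, as percent of days.** The early-only difference gives 10, 0 and 0 points. The constant rate gives 10%, 10% and 10%.

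**The case against.** Four objections carry weight.

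1. *The model handles correlation.* A reader might infer that the same days enter twice as if independent, so that the standard errors are wrong. The documents do not support that: the mixed model is chosen to account for correlation over time and can absorb the part that overlap adds. It cannot change what the week-12 score measures.
2. *The comparison is randomized.* A reader might infer that the week-12 arm comparison is invalid. It is not. It compares the arms over roughly the first 12 weeks after discharge, and the plan nowhere says that week 12 isolates weeks 7-12. But it does not call week 12 cumulative either.
3. *Effects are not halved.* A reader might infer that an early benefit reappears at half size. That would hold only for windows cut at discharge and rescored as percent of days (4.2/42 = 10% against 4.2/84 = 5%). The planned scores are day counts and percents with a 90-day base, on which the early difference reappears in full.
4. *Coverage is complete on schedule.* This is true. A missed week-12 visit leaves days 43-78 unobserved (36 days), and a week-24 visit more than 6 days late leaves a shorter gap. This is ordinary missing data, for which the plan has attrition analyses and multiple imputation. It is a secondary matter.

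Aims 2-4 are also secondary and preliminary in a pilot of 60 dyads. That limits the seriousness, but a pilot meant to inform a larger trial gains from knowing when an effect occurs.

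**Conclusion.** The point holds for the week 6/week 12 pair of 90-day counts: days of use and abstinence, the SFS, and the school, legal and sexual-behavior counts. On schedule, 48 of 90 days are shared and all 42 post-discharge days of week 6 are counted again. The week-12 result is cumulative, and the week 6-to-12 change does not compare weeks 7-12 with weeks 1-6.

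The overlap does not materially affect week 24. Nor is it shown to affect latency to first use, recency of last sex, urine screens, the PMQ, the PACS or the FAsTask, which are not 90-day counts as described.

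The conclusion assumes visits close to schedule and the full 90-day recall at follow-up, which is the only recall the documents describe. The 4.2, 8.4 and 9.0 figures rest on the assumed rates, and for the constant-rate series also on no counted use before discharge. This should be corrected before analysis; it does not invalidate the randomized comparisons.

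**What to change.** - **Calendar-based day counts** (substance use days, and school days, for which the plan calls the method comparable): score each follow-up as percent of days in the interval since discharge or the last scheduled visit, namely days 1-42, 43-84 and 85-168. Percent is needed because the intervals last 42, 42 and 84 days. Use these scores in the mixed models. On-schedule 90-day calendars already cover all three intervals.
- **Late or missed visits:** mark the last interview date on the calendar and extend the calendar back to it. After a missed week-12 visit, the week-24 calendar would span days 43-168, or 126 days.
- **Items that cannot be split by date** (for example number of partners, and any SFS component without dated days): add a since-last-interview prompt, or report week 12 explicitly as cumulative and do not interpret the week 6-to-12 change.
- **Norms:** keep the standard 90-day SFS and other 90-day scores for the planned comparison with GAIN norms.

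The cost is a scoring rule, one added interviewer prompt and two versions of some scores. Interval scores are not directly comparable with published 90-day norms, and recall is longer after a missed visit. The documents describe a calendar but do not say that dated use days are retained. Confirm this first, since the GAIN data go into proprietary software.
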